1.1 Baseline characteristics

Summary statistics will be provided by treatment group for demographics and baseline characteristics. Continuous variables will be summarized using n, mean, standard deviation or median, 25'th and 75' percentile depending on distribution of data. Categorical variables will be summarized using frequency and percentage. The difference between treatment groups will be compared using the Chi-square test, t-test or Mann-Whitney, as appropriate. A p value <0.05 will be considered statistically significant.

1.2 Analysis of primary endpoint

Primary endpoint, PCWP/CI ratio, will be analyzed using ANCOVA or mixed effects models with treatment as fixed effect factor with the intention-to-treat principle. Additionally, the baseline value of the corresponding variable may be included as a covariate if appropriate. The estimated treatment effect and the corresponding two-sided 95% confidence interval will be provided.

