The main objective of this study is to assess the effect of angiotensin–neprilysin inhibition on central hemodynamics, myocardial structure and myocardial function in patients with a recent AMI and Doppler echocardiographic signs of diastolic dysfunction and preserved systolic function.

5.1 Primary objective:

To assess the effect of 6 months treatment with LCZ696 compared with placebo on ratio of PCWP/CI during exercise in patients with a recent AMI and Doppler echocardiographic signs of diastolic dysfunction and preserved systolic function.

5.2 Secondary objectives:

To assess the effect of 6 months treatment with LCZ696 compared with placebo in patients with a recent AMI and Doppler echocardiographic signs of diastolic dysfunction and preserved systolic function on:

1. Cardiac fibrosis assessed on cardiac magnetic resonance imaging,
2. The ST2 cardiac biomarker
3. Left atrial size and function
4. MR-proANP and NT-proBNP
5. Diastolic dysfunction assessed by Doppler echocardiography

5.3 Primary endpoint:

Ratio of pulmonary capillary wedge pressure to cardiac index at peak exercise after 26 weeks treatment with LCZ696 or placebo.

5.4 Secondary endpoints:

1. Amount of hyperenhancement on cardiac MRI using a semiquantitative assessment of late gadolinium hyperenhancement in a 17 segment model of the LV.
2. ST2 concentration at rest.
3. Left atrial volume by echocardiography and left atrial emptying fraction by echocardiography at rest.
4. MR-proANP and NT-proBNP concentration at rest.
5. Proportion of patients with moderate or severe diastolic dysfunction at rest.

6 Methodology:

The ARNiAMI study is a prospective, multicenter, randomized, double blind clinical trial to evaluate the efficacy, of LCZ696 97/103 mg BID versus matching placebo in subjects aged 50 years or older with a recent documented AMI, diastolic dysfunction and LVEF $\geq 45\%$ on cardiac physiology and myocardial fibrosis. Patients who meet the study inclusions and none of the exclusion criteria will after signing an Ethics Committee approved Informed Consent Form, be asked to undergo baseline procedures for the study.

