Patients will be randomized in a 1:1 double-blind trial to receive LCZ696 or matching placebo using a computer-generated randomization schedule. Randomization will be stratified by PWCP at rest. Production of study medication, matching placebo, packing and handling of study medication will be performed by Sygehusapotek Fyn. Study medication will be delivered to the participating centers in blinded containers. Containers will be labeled with a unique identification number. Randomization will be performed by the investigator and a randomization number is assign to the patient. When dispensing study medication container ID's is requested from Sygehusapotek Fyn via E-mail. The randomization codes will be kept in sealed envelopes with the Trial Master file and will not be opened before the study has ended. The randomization schedule will also be available through a password protected online form. In case of emergent need for unblinding the coordinating investigator will be contacted pr. telephone and treatment allocation is unblinded either through the online form (with a dedicated user for this purpose with strict logging) or sealed envelopes. Compliance will be assessed using pill count.

The study will be performed according to ICH-GCP. The ethics Committee for the Region of Southern Denmark will be applied for ethical approval and the study will be registered at ClinicalTrials.gov. All patients will provide written informed consent.

6.1 Justification of key elements of study design:

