6.1.3 Sample size

Based on previous data it is expected that PCWP will increase to 32 ± 8 mmHg and cardiac index to 7.4 ± 1.4 l/min/m², with a PCWP/CI ratio of 4.49 ± 1.4 (19).

To detect a decrease of 20% in primary endpoint with alpha of 0.05 and beta 0.8, a total of 90 patients are required, to allow 10% dropout rate 100 patients are expected to be enrolled.

| Difference in PCWP/CI ratio | Standardized difference | N (Total) $\alpha=0.05/\beta=0.8$ | N (Total) $\alpha=0.05/\beta=0.9$ |
|-----------------------------|-------------------------|--------------------------------------|--------------------------------------|
| 10% (0.449) | 0.299 | 320 | 450 |
| 15% (0.674) | 0.449 | 150 | 200 |
| 20% (0.898) | 0.598 | 90 | 110 |
| 25% (1.12) | 0.748 | 70 | 100 |

7 Timelines and Study duration:

Start date: June 2018

Approval from relevant authorities: Medio august 2018

Inclusion start: 1/9 2018

Last patient last visit: July 2020

End date: July 2020

Clinical study report date: August 2020

Publication date: September 2020 – May 2021

8 Population:

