^a Unblinded measurements: Hemoglobin, platelet count, white blood cell count(WBC), WBC differential, alanine aminotransferase (ALT), albumin, total bilirubin, alkaline phosphatase, blood urea nitrogen, calcium, creatinine, potassium, sodium, glucose, lipid profile(total cholesterol, LDL, HDL and triglycerides). Additional blood samples are drawn and stored for later analysis of NT-proBNP, MR-pro-ANP, ST2 and possible future biomarkers.

Patients who meet the study inclusions and none of the exclusion criteria will after signing an Ethics Committee approved Informed Consent Form, will undergo conventional spirometry, blood testing, comprehensive resting Doppler echocardiography, cardiac MRI with late enhancement imaging, resting right heart catheterization, and symptom-limited supine cycle exercise test with simultaneous echocardiography and right heart catheterization will be performed before randomization.

After randomization patients will be started on LCZ696 49/51 mg twice daily or matching placebo twice daily titrated to their final doses of LCZ696 97/103 mg twice daily or matching placebo twice daily over a period of 2–4 weeks. Succeeding up titration to final dose a visit is planned after two weeks (visit 2) to assess tolerability. In case of clinical concern regarding tolerability additional follow up is left at discretion of the investigator.

Background therapy will be decided at the discretion of treating physicians. The double-blind design will continued for 26 weeks. After 26 weeks treatment cardiac MRI, echocardiography, right heart catheterization and exercise test will be repeated.

Patients will in addition to the above mentioned be followed in the “Prevention and aftercare out-patient clinic” as per standard care following AMI.

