15.2 Analysis of primary endpoint

Primary endpoint, PCWP/CI ratio, will be analyzed using ANCOVA with treatment as fixed effect factor. Additionally, the baseline value of the corresponding variable may be included as a covariate if appropriate. The estimated treatment effect and the corresponding two-sided 95% confidence interval will be provided.

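### Adjustment of the primary analysis for baseline peak PCWP/CI is left optional although the value is collected; requiring it in one named model would narrow the confidence interval compared with the unadjusted analysis the text permits

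*SAP*

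**What the plan says.** The endpoint is fixed. Protocol 5.3 defines it as "Ratio of pulmonary capillary wedge pressure to cardiac index at peak exercise after 26 weeks treatment with LCZ696 or placebo".

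The model is not. Protocol 15.2 says the ratio "will be analyzed using ANCOVA with treatment as fixed effect factor". SAP 1.2 widens this: the ratio "will be analyzed using ANCOVA or mixed effects models with treatment as fixed effect factor with the intention-to-treat principle". Treatment is the only term that either document requires. Both then make baseline optional in the same words; the SAP reads "Additionally, the baseline value of the corresponding variable may be included as a covariate if appropriate". No criterion for the decision is given. The SAP also gives no rule for choosing between ANCOVA and a mixed model, and no random effects, time terms or covariance structure for the latter.

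The baseline value will exist. Protocol 11 states that the "symptom-limited supine cycle exercise test with simultaneous echocardiography and right heart catheterization will be performed before randomization", and Protocol 11.2 records cardiac output and PCWP at every exercise level.

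Protocol 6 adds: "Randomization will be stratified by PWCP at rest". Neither analysis section mentions this stratification factor.

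**The concern.** An ANCOVA whose only required term is treatment is a two-group comparison of week-26 means. The text allows that analysis even though each patient has had an invasive baseline measurement of the same quantity. If baseline and week-26 ratios are correlated, leaving baseline out makes the interval wider and the power lower than the collected data can give.

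The primary result carries more than itself, because SAP 1.3 allows inference on the five secondary variables only if the primary hypothesis is rejected. A primary result missed through avoidable imprecision would close those as well.

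The smaller part of the point is the stratification factor. A factor used to balance the randomisation would normally be in the model, but it should add little once baseline peak PCWP/CI is there.

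**Working it through.** **Inputs from the documents.** Protocol 6.1.3: mean ratio 4.49, SD 1.4; target difference 20%, that is 0.20 × 4.49 = 0.898; alpha 0.05; 90 patients, raised to 100 for 10% dropout; printed standardised difference 0.598. SAP 1.2: two-sided 95% interval. Protocol 6: 1:1 allocation. I therefore use n = 45 evaluable per arm.

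**Assumed.** The correlation r between baseline and week-26 peak PCWP/CI is not in the documents. I take 0.3, 0.5 and 0.7.

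**Step 1: reproduce the planned size.** The protocol states: "To detect a decrease of 20% in primary endpoint with alpha of 0.05 and beta 0.8, a total of 90 patients are required" (its beta of 0.8 is read as power). The printed standardised difference implies SD = 0.898/0.598 = 1.50, not the stated 1.4. An unadjusted two-sample t-test at SD 1.5 needs 45 per arm, 90 in total, and 90/0.9 = 100. The plan's figure reproduces as an unadjusted comparison. With SD 1.4 the t-test needs 80.

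**Step 2: unadjusted precision at SD 1.5.**
- SE = 1.5 × √(2/45) = 0.316.
- Half-width = 1.987 × 0.316 = 0.628 (88 df).
- Noncentrality = 0.898/0.316 = 2.84; power 80.2%.

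**Step 3: baseline-adjusted precision.** The residual SD is 1.5 × √(1 − r²). One degree of freedom is lost (87 df, t = 1.988). Estimating the slope multiplies the SE by √(1 + 1/(2n − 4)) = √(1 + 1/86) = 1.0058. At r = 0.5, for example:
- Residual SD = 1.5 × √0.75 = 1.299.
- SE = 1.299 × √(2/45) × 1.0058 = 0.275.
- Half-width = 1.988 × 0.2754 = 0.547.

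| r (assumed) | Residual SD | Half-width | Narrower by | Power for 0.898 |
|---|---|---|---|---|
| unadjusted | 1.500 | 0.628 | – | 80.2% |
| 0.3 | 1.431 | 0.603 | 4% | 83.3% |
| 0.5 | 1.299 | 0.547 | 13% | 89.7% |
| 0.7 | 1.071 | 0.451 | 28% | 97.4% |

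With the stated SD of 1.4 the half-width goes from 0.587 to 0.563, 0.511 or 0.421, and power from 85.3% to 88.0%, 93.2% or 98.7%.

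**Step 4: where the gain stops.** Adjustment narrows the expected interval when 1.988 × √(1 − r²) × 1.0058 is below 1.987. That requires |r| above about 0.11. Below that, the lost degree of freedom and the slope estimation cancel the gain.

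**Step 5: how often the verdict changes.** I simulated 100,000 trials per value of r, with 45 per arm, a true difference of 0.898, SD 1.5 and no stratification. The two analyses compared are the unadjusted and the baseline-adjusted regressions. They disagree on significance in about 7%, 12% and 18% of trials at r = 0.3, 0.5 and 0.7. Only the adjusted analysis is significant in about 5%, 11% and 17.5%. This is the power difference of step 3 seen as a verdict, not a further harm.

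**Step 6: type I error.** Under the null, each analysis alone holds 5%. If the smaller of the two p-values were reported, the rate would be about 6.3%, 7.3% or 8.2%. No mixed model was simulated, because the plan does not specify one.

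**The case against.** The strongest reply is that the comparison takes the least favourable reading. Both documents say ANCOVA, and the only covariate either names is the baseline value. ANCOVA without it is a t-test, which neither document mentions. If the sponsor intends to use the option already written, nothing is gained. That stands as a limit: the figures measure the fix against an analysis the text permits, not one it states. It does not remove the point, because the sentence that names the covariate also makes it optional.

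Second, the gain depends on an assumed correlation. At r = 0.3 it is modest: a 4% narrower interval and three points of power. That stands too.

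Third, ranking ANCOVA above a mixed model is a preference. A mixed model with a common baseline mean also uses the baseline information, and it can keep patients who have a baseline but no week-26 value. This stands; what matters is that one model is named and that it uses baseline.

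Two stronger readings are tempting. A reader might infer that the choice between ANCOVA and a mixed model itself moves the result by the amounts shown. The documents do not specify the mixed model, so no such size can be given; the disagreement rates concern unadjusted against baseline-adjusted regression only. A reader might also infer an inflated type I error, since the SAP is version 1 dated 07022024 and Protocol 7 planned the last visit for July 2020. Inflation needs the smaller p-value to be picked after results are seen. The documents show neither that nor the actual visit dates or blinding status.

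**Conclusion.** The point holds as one of precision and clarity, and it should be fixed. Relative to the unadjusted analysis the text permits, requiring baseline peak PCWP/CI would narrow the expected interval by 4% to 28%. This rests on 45 evaluable per arm, SD 1.5 and an assumed r of 0.3 to 0.7; the direction is the same at SD 1.4. The narrowing is an expectation, not a guarantee in one dataset.

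The unadjusted analysis is not biased and keeps the planned power, so the trial is not underpowered on its own terms. The wording gap is certain from the text. The size of the gain is not, because r is undocumented. Omission of the resting-PCWP stratum is minor.

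**What to change.** In SAP 1.2, with Protocol 15.2 referring to it:

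- Delete *may* and *if appropriate*. Name one primary model for week-26 peak PCWP/CI, with treatment, baseline peak PCWP/CI as a continuous covariate, and the resting-PCWP randomisation stratum.
- ANCOVA is the simplest choice and matches the protocol. A mixed model with a common baseline mean across arms, reporting the week-26 contrast, is acceptable if it is named as the single primary model. Whichever is not chosen becomes a sensitivity analysis.
- Make the change before unblinding. If results are already known, say when the model was chosen and report the baseline-adjusted ANCOVA alongside it.

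The cost is wording and a few degrees of freedom; the exact number depends on how many strata were used, which the documents do not say. No new data or visits are needed. The downside is no expected gain in the interval if |r| is below about 0.11.

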1.3 Analysis of secondary endpoints

The secondary hypotheses will be tested and statistical inferences will be made only if the primary hypothesis is rejected. The five secondary efficacy variables will be tested for superiority of LCZ696 to placebo for all randomized patients following the intent-to-treat principle.

Version: 1

Date 07022024
